6.15.4.1. Leukocytes (WBC) and Platelets

Further analyses will be conducted for total leukocytes, neutrophils, platelets, lymphocytes, monocytes, eosinophils, and basophils. Neutrophils will be defined as absolute neutrophils (derived by adding segmented neutrophils and band neutrophil). Shift table will be produced showing the number and percentage of patients shifting from baseline to a minimum post-baseline result in each relevant category by treatment group for Period 2, Period 3 and Period 4, respectively.

- Scheduled visits, unscheduled visits, and repeated measurements taken at the same visit will be included.
- Baseline is defined as the minimum result during the defined baseline period or baseline.
- Use the minimum non-missing post-baseline value within each study period.
- The parameters and categories are:
 - Leukocytes; $\geq 1 \times \text{LLN}$, $< 1 \times \text{LLN}$ to $\geq 3.0 \times 10^9/\text{L}$, $< 3.0 \times 10^9/\text{L}$ to $\geq 2.0 \times 10^9/\text{L}$, $< 2.0 \times 10^9/\text{L}$ to $\geq 1.0 \times 10^9/\text{L}$, and $< 1.0 \times 10^9/\text{L}$
 - Neutrophils (absolute neutrophils); $\geq 1 \times \text{LLN}$, $< 1 \times \text{LLN}$ to $\geq 1.5 \times 10^9/\text{L}$, $< 1.5 \times 10^9/\text{L}$ to $\geq 1.0 \times 10^9/\text{L}$, $< 1.0 \times 10^9/\text{L}$ to $\geq 0.5 \times 10^9/\text{L}$, and $< 0.5 \times 10^9/\text{L}$
 - Platelets; $\geq 1 \times \text{LLN}$, $< 1 \times \text{LLN}$ to $\geq 75.0 \times 10^9/\text{L}$, $< 75.0 \times 10^9/\text{L}$ to $\geq 50.0 \times 10^9/\text{L}$, $< 50.0 \times 10^9/\text{L}$ to $\geq 25.0 \times 10^9/\text{L}$, and $< 25.0 \times 10^9/\text{L}$
 - Lymphocytes; $\geq 1 \times \text{LLN}$, $< 1 \times \text{LLN}$ to $\geq 0.8 \times 10^9/\text{L}$, $< 0.8 \times 10^9/\text{L}$ to $\geq 0.5 \times 10^9/\text{L}$, $< 0.5 \times 10^9/\text{L}$ to $\geq 0.2 \times 10^9/\text{L}$, and $< 0.2 \times 10^9/\text{L}$
- The above LLNs are defined as:
 - Leukocytes: $\text{LLN} = 4.0 \times 10^9/\text{L}$
 - Neutrophils: $\text{LLN} = 2.0 \times 10^9/\text{L}$
 - Lymphocytes: $\text{LLN} = 1.1 \times 10^9/\text{L}$
 - Platelets: $\text{LLN} = 150 \times 10^9/\text{L}$
- With additional categories:

- Decreased; post-baseline category < baseline category
- Increased; post-baseline category > baseline category
- Same; post-baseline category = baseline category.

The change from minimum baseline to minimum post-baseline result for each of these leukocytes and platelets will be summarized graphically using a box plot for Period 2, Period 3, and Period 4, respectively.

6.15.4.2. Neutrophil Follow-up

Neutrophil counts will be followed throughout the study. Patients will continue in Period 4 until their neutrophil counts have recovered.

The neutrophil follow-up analysis will be conducted on the neutrophil follow-up population defined as patients who have an absolute neutrophil count <1500 cells/ μ L (SI units: $<1.5 \times 10^9/L$) at the last scheduled visit or early termination visit prior to entering the Post-Treatment Follow-up Period (Period 4) and less than the patient's baseline absolute neutrophil count (that is, prior to first injection at Week 0). These patients are monitored during the Period 4 until neutrophil recovery.

Neutrophil clinical recovery is defined as an absolute neutrophil count ≥ 1500 cells/ μ L (SI units: $\geq 1.5 \times 10^9/L$) or greater than or equal to a patient's minimum absolute neutrophil count prior to first study drug injection at Week 0.

If a patient's neutrophil count has not recovered, within 12 weeks after entering the follow-up period (Visit 802), the patient will return for Visit 803 (12 weeks after Visit 802). Additional visits may be required for appropriate patient management depending upon the degree of neutropenia. If at Visit 802, a patient's has met the criteria for neutrophil recovery, the patient's participation in the study will be considered complete unless the investigator deems additional follow-up may be necessary.

The number and percentage of patients achieving neutrophil clinical recovery will be presented by treatment group and week interval for neutrophil follow-up population for Post-Treatment Follow-up Period (Period 4). The number and percentage of patients with an absolute neutrophil cell count that is at least 25%, 50%, 75%, or 100% of the patient's baseline absolute neutrophil count (that is, prior to first injection at Week 0), irrespective of absolute neutrophil minimum, will be included in the summary.

6.15.5. Vital Signs and Other Physical Findings

Analyses will be conducted on vital signs and physical characteristics including systolic blood pressure (mm Hg), diastolic blood pressure (mm Hg), pulse (bpm), weight (kg), body mass index (BMI) (kg/m^2), and waist circumference (cm). By-patient listings of vital signs and physical characteristics will be provided.

Change from baseline to last observation for vital signs and physical characteristics will be summarized for patients who have both baseline and at least one post-baseline result, for Period 2, Period 3 and Period 4, respectively:

The scheduled visits/measurements will be included. The unscheduled visits and the repeated measurements taken at the same visit will be excluded.

- For the safety population in the Blinded Treatment Period (Period 2), the comparisons between treatment groups will be conducted using an ANCOVA with treatment group and baseline value in the model.
- Data will be analyzed based on original scale.

For vital signs and physical characteristics, the observed values at each visit (starting at baseline) and change from baseline to each scheduled visit, respectively, will be displayed in box plots for patients who have both a baseline and at least one post-baseline result. These box plots will be used to evaluate trends over time and to assess a potential impact of outliers on central tendency summaries.

- The scheduled visits/measurements will be included. The unscheduled visits and the repeated measurements taken at the same visit will be excluded.
- The following summary statistics will be included as a table below the box plot: number of patients with a baseline and at least one post-baseline result, mean, standard deviation, minimum, Q1, median, Q3, and maximum.
- Data will be summarized based on original scale.

To assess the effect of administration of study drug on vital signs (blood pressures and pulse rate) among patients, at Week 0, vital signs will be measured before the first injection and 1 hour after the injection. The box plots will be produced for pre-dose and post-dose vital signs at Week 0 (Visit 2) by treatment group for safety population.

The number and percentage of patients with treatment-emergent or follow-up emergent high or low vital sign and weight at any time for Period 2, Period 3 and Period 4, respectively, will be summarized. The comparisons between treatment groups will be conducted using Fisher's exact test for the safety population for the Blinded Treatment Period (Period 2).

- [Table RHBQ.6.7](#) defines the high and low baseline values as well as the limits that are specified as treatment-emergent and follow-up emergent. Note that weight does not have an abnormal baseline; therefore, the treatment-emergent and follow-up emergent values are determined by change from baseline.
- All post-baseline scheduled, unscheduled and repeated measurements at the same visit will be included.
- To assess increases, change from the maximum value during the baseline period or baseline to the maximum value during each study period will be used.

- To assess decreases, change from the minimum value during the baseline period or baseline to the minimum value during each study period will be used.
- For treatment-emergent high and low:
 - A treatment-emergent high result is defined as a change from a value less than or equal to the high limit at baseline to a value greater than the high limit at any time that meets the specified change criteria during the respective treatment periods.
 - A treatment-emergent low result is defined as a change from a value greater than or equal to the low limit at baseline to a value less than the low limit at any time that meets the specified change criteria during the respective treatment periods.
- For follow-up emergent high and low:
 - A follow-up emergent high result is defined as a change from a value less than or equal to the high limit at baseline to a value greater than the high limit at any time that meets the specified change criteria during the Post-Treatment Follow-up period.
 - A follow-up emergent low result is defined as a change from a value greater than or equal to the low limit at baseline to a value less than the low limit at any time that meets the specified change criteria during the Post-Treatment Follow-up period.

Table RHBQ.6.7. Categorical Criteria for Abnormal Treatment-Emergent Blood Pressures and Pulse Measurement, and Categorical Criteria for Weight Changes for Adults

Parameter	Low	High
Systolic BP (mm Hg) ^a (supine or sitting – forearm at heart level)	≤90 and decrease from baseline ≥20	≥140 and increase from baseline ≥20
Diastolic BP (mm Hg) ^a (supine or sitting – forearm at heart level)	≤50 and decrease from baseline ≥10	≥90 and increase from baseline ≥10
Pulse (bpm) ^a (supine or sitting)	<50 and decrease from baseline ≥15	>100 and increase from baseline ≥15
Weight (kg)	(Loss) decrease from baseline ≥7%	(Gain) increase from baseline ≥7%

Abbreviations: BP = blood pressure; bpm = beats per minute; kg = kilogram; mm Hg = millimeters of mercury.

^a Baseline abnormal values are defined by the value presented.

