Appendix 2. Schedule of Activities

Schedule of Activities, Protocol I1F-MC-RHBQ

CRF Visit (V) Number	Screening		Baseline Randomization	Blinded Treatment Period (Period 2)				
	V1		V2	V3	V4	V5	V6	V7
Weeks since Randomization			W0	W1	W2	W4	W8	W12
Study Days	-30 to -7 d	V1A: 2-3 d post-V1	1	7 ± 2d	14 ± 2d	28 ± 2d	56 ± 2d	84 ± 4d
Informed consent	X							
Complete medical history	X							
Demographics ^a	X							
Sociodemographics ^b			X					X
Physical examination ^c	X		X					X
Perianal/gluteal cleft characteristics examination	X		X					X
Inclusion/exclusion criteria ^d	X		X					
Body temperature			X					
Height			X					
Weight			X					X
Waist circumference			X					
Vital signs (BP and pulse)	X		X ^e	X	X	X	X	X ^e
Consumption habits ^f			X					
Concomitant medications	X		X	X	X	X	X	X
Review preexisting conditions/AEs			X	X	X	X	X	X
Randomization			X					
Administer IP on site			X					X

	Screening		Baseline Randomization	Blinded Treatment Dosing Period (Period 2)				
CRF Visit (V) Number	V1		V2	V3	V4	V5	V6	V7
Weeks since Randomization			W0	W1	W2	W4	W8	W12
Study Days	-30 to -7 d	V1A: 2-3 d post-V1	1	7 ± 2d	14 ± 2d	28 ± 2d	56 ± 2d	84 ± 4d
Dispense IP			X		X	X	X	X
Provide SDALg			X		X	X	X	X
Collect, review, and enter data from SDAL			X		X	X	X	X
Review e-diary				X	X	X	X	X
Dispense e-diary (includes GPSS, GPSIS, and SFQ)	X							
Collect e-diary								X
Clinical Efficacy/Health Outcomes								
sPGA (overall)	X		X	X	X	X	X	X
sPGA of Genitalia ^h	X		X	X	X	X	X	X
PASI (overall)	X		X	X	X	X	X	X
mGPASI ⁱ	X		X	X	X	X	X	X
BSA	X		X ^j	X	X	X ^j	X	X ^j
Fitzpatrick skin type			X					
GPSS ^k	Daily from Screening (V1) to Week 12 (V7)							X
GPSIS ^k	Weekly from Screening (V1) to Week 12 (V7)							X
SFQ ^k	Weekly from Screening (V1) to Week 12 (V7)							X
PatGA-Genital			X	X	X	X	X	X
Touch avoidance NRS			X		X	X	X	X

CRF Visit (V) Number	Screening		Baseline Randomization	Blinded Treatment Dosing Period (Period 2)				
	V1		V2	V3	V4	V5	V6	V7
Weeks since Randomization			W0	W1	W2	W4	W8	W12
Study Days	-30 to -7 d	V1A: 2-3 d post-V1	1	7 ± 2d	14 ± 2d	28 ± 2d	56 ± 2d	84 ± 4d
SF-36			X					X
DLQI			X		X	X	X	X
QIDS-SR16	X		X					X
C-SSRS [§]			X	X	X	X	X	X
Self-Harm Supplement Form [§]			X	X	X	X	X	X
CAPP (genital subindex)			X					X
Laboratory Tests								
Administer PPD/QuantiFERON [®] -TB Gold/T-SPOT [®] 1	X							
Read PPD		X						
Chest x-ray ^m	X							
ECG	X							
HIV/HCV	X							
HBV ⁿ	X		X					X
FSH ^o	X							
Serum pregnancy test ^p	X							

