- ^u Immunogenicity samples may also be analyzed for ixekizumab serum concentration to facilitate in the interpretation of the immunogenicity data. In addition, a blood sample will be collected, when possible, for any patient who experiences a potential systemic allergic/hypersensitivity reaction during the study as judged by the investigator (Section 8.4.6).
- ^v At visits where dosing is scheduled, PK samples will be collected prior to administration of investigational product (Section 8.5).
- ^w Swab from labia majora for women and glans penis for men.
- ^x All patients receiving investigational product must enter into Period 4 and complete through Visit 802. Patients may be followed beyond Visit 802 for continued monitoring of their neutrophil counts or for other safety reasons.
- ^y If a patient discontinues study treatment early, the patient will complete the ETV and then enter the Post-Treatment Follow-Up Period.
- ^z This visit will only occur if a patient's neutrophil counts have not returned to the criteria defined in Section 8.4.9.1 or for other safety reasons.
- [§] A Self-Harm Follow-Up Form is to be completed for each discrete self-harm event identified on the C-SSRS and the Self-Harm Supplement Form.

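### SAP 6.15.5 plans a Period 2 waist-circumference comparison and Period 4 weight, BMI and waist changes that the Schedule of Activities cannot supply

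*SAP*

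**What the plan says.** SAP 6.15.5 names six parameters: systolic and diastolic blood pressure, pulse, weight, BMI and waist circumference. It then treats them as one list:

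- "Change from baseline to last observation for vital signs and physical characteristics will be summarized for patients who have both baseline" plus a later value, separately in each of Periods 2, 3 and 4.
- For the safety population in Period 2, "the comparisons between treatment groups will be conducted using an ANCOVA with treatment group and baseline value in the model".
- For the change analysis and the box plots, "The unscheduled visits and the repeated measurements taken at the same visit will be excluded".
- Separately, a categorical analysis counts patients with "treatment-emergent or follow-up emergent high or low vital sign and weight at any time for Period 2, Period 3 and Period 4". That analysis takes in unscheduled and repeated values as well, and its list stops at vital signs and weight.

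Protocol Appendix 2 has its own row for "Waist circumference", with a mark at Visit 2 in the first half of the schedule and at Visit 12 and the ETV in the second half. On who attends the ETV, a footnote says: "If a patient discontinues study treatment early, the patient will complete the ETV and then enter the Post-Treatment Follow-Up Period".

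**The concern.** The analysis list and the measurement schedule do not match. Someone who completes Week 12 has no scheduled post-baseline waist value in Period 2, so the requirement for a post-baseline result quietly removes every completer. If anyone remains, it is because they discontinued, which happens after randomisation and may depend on treatment. A p-value from that subset would have no randomised interpretation, although it would sit in the same table as the valid weight and blood pressure comparisons.

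In Period 4 the risk is one of reading. A change table for weight, BMI and waist with no scheduled measurements behind it could be taken as evidence of no change when nothing was systematically measured.

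**Working it through.** The plan gives no figure for this point. Its one stated design figure, 94% power with 73 per arm at 2% versus 20%, reproduces (94.7% by exact enumeration of the two-sided Fisher test), but nothing here depends on it. Only the total of 146 is used below.

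**Step 1. Schedule against analysis** (Protocol Appendix 2 against SAP 6.15.5)

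| Parameter | Period 2, after Visit 2 | Period 3 | ETV | Visits 801–803 |
|---|---|---|---|---|
| Waist | none | Week 52 | yes | none |
| Weight (and so BMI) | Week 12 | Week 52 | yes | none |
| Blood pressure, pulse | every visit | every visit | yes | every visit |

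The waist row has the same layout as the height row above it, and no footnote adds a measurement, so this does not look like a table-extraction fault.

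**Step 2. Period 2 waist set.** Scheduled post-baseline values per Week 12 completer: 0. Per early terminator: 1 if the ETV counts as scheduled, 0 if it does not. The set therefore lies between 0 and the number of Period 2 discontinuations who attend an ETV.

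**Step 3. Size.** The documents give no discontinuation rate, so 5% to 15% is an assumption.

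- 146 × 0.05 = 7.3
- 146 × 0.15 = 21.9

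That is about 7 to 22 patients across both arms. A wider assumption of 3% to 20% gives 146 × 0.03 = 4.4 to 146 × 0.20 = 29.2, about 4 to 29.

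**Step 4. What such a set could detect.** Standardised difference at 80% power, two-sided 0.05, no baseline adjustment and discontinuations split equally: (1.96 + 0.84) × √(2/n per arm).

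- n = 73 per arm: 0.46 SD
- n = 10.95 per arm (15%): 1.20 SD
- n = 3.65 per arm (5%): 2.07 SD

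So the comparison would be uninformative even if selection were ignored.

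**Step 5. Period 4.** SAP 6.1.2 sets the follow-up baseline at the last value up to Week 52 or the ETV, so that value cannot also be the post-baseline one. Scheduled values after it: weight 0, BMI 0, waist 0.

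**Step 6. Which baseline applies to Period 3 waist.** SAP 6.1.2 takes the last non-missing value up to Week 12. SAP 6.15 gives a rule for changes to last observation in laboratory and vital-sign data: the last value in the baseline period, which ends at the first injection. With no Week 12 waist value, both lead to the pre-treatment value, normally Week 0. The SAP does not say which rule governs, and 6.15.5 names physical characteristics separately from vital signs.

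**The case against.** The mismatch in the schedule is hard to dispute. The fair objections concern how much follows from it.

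- **A biased Period 2 p-value.** A reader might infer that one will certainly be produced. The documents do not settle this. SAP 6.15.4.2 and Protocol 8.4.9.1 name the ETV as something distinct from the last scheduled visit, and SAP 6.15.5 excludes unscheduled visits. On that reading the set is empty and there is no test. SAP 6.1 points the other way, because it keeps off-schedule ETV data in analyses other than MMRM. This objection stands: the claim is what the set could contain, not what it will contain.
- **A mislabelled Period 3 interval.** A reader might infer that waist change is wrongly presented as a 40-week change. The SAP never labels it so, and under the SAP 6.15 rule Week 0 is the baseline by design. What remains is a need to say which rule applies.
- **An empty Period 4 weight table.** A reader might infer that the categorical weight analysis is empty by design. It is not, because that analysis accepts unscheduled weights. The gap is in the change-from-baseline summaries and box plots. The box-plot tables also print the number of patients, which partly guards against misreading.
- **Materiality.** Protocol 9.6.3 asks only for a descriptive summary of covariates such as body weight and does not mention waist. One general sentence applied to a parameter list may simply yield blank cells. That is true, and it is why the point is small. But the same section leaves waist and BMI out of its categorical analysis, so restricting by parameter is already within its style.

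**Conclusion.** The concern holds in a limited form. Followed as written, SAP 6.15.5 calls for a Period 2 between-arm test on waist circumference that can include only early terminators with an ETV, or no one. It also calls for Period 4 change summaries of weight, BMI and waist with no scheduled measurements.

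The absence of marks in the schedule is read directly from the protocol. The size of the Period 2 set is not: it is 0 up to the number of Period 2 discontinuations, and 7 to 22 of 146 rests on the assumed 5% to 15%.

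This is a minor safety-descriptor issue. The primary endpoint, alpha, power, Period 2 weight and BMI, and all blood pressure and pulse analyses are unaffected.

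**What to change.** Amend SAP 6.15.5 only; the protocol need not change.

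- Remove waist circumference from the Period 2 ANCOVA, summary and box plots.
- Remove weight, BMI and waist from the Period 4 change-from-baseline summaries and box plots.
- Summarise waist once, descriptively and by randomised group, as change from Week 0 to last observation through Week 52. Include ETV values, so that patients who stop early are not dropped, and label the output with its baseline.
- State which baseline rule, SAP 6.1.2 or SAP 6.15, governs these changes.
- Keep any unscheduled Period 4 weights in the categorical table or the listing, with the number of patients actually measured as the denominator.

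The cost is a wording change and the loss of one between-arm comparison and some tables that would be empty or nearly so.

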6.15.6. Quick Inventory of Depressive Symptomatology–Self Report 16items (QIDS-SR16)

The QIDS-SR16 is a self-administered 16-item instrument intended to assess the existence and severity of symptoms of depression as listed in the American Psychiatric Association's (APA's) *Diagnostic and Statistical Manual of Mental Disorders, 4th Edition (DSM-IV)* (APA 1994). The QIDS-SR16 scale is used to assess the potential impact of treatment on new onset or changes in depression, thoughts of death, and/or suicidal ideation severity. A patient is asked to consider each statement as it relates to the way they have felt for the past 7 days. There is a 4-point scale for each item ranging from 0 to 3. The 16 items corresponding to 9 depression domains are summed to give a single score ranging from 0 to 27, with higher scores denoting greater symptom severity. Additional information and the QIDS-SR16 questions may be found at the University of Pittsburgh IDS/QIDS resource page (2015 [WWW]).

The 9 domains assessed by the instrument are defined as:

- 1) Sleep disturbance (initial, middle, and late insomnia or hypersomnia): the highest score recorded for the four sleep items: #1 (falling asleep), #2 (sleep during the night), #3 (waking up too early) and #4 (sleeping too much). This domain is missing if all items are missing.
- 2) Sad mood: Item #5 (feeling sad). This domain is missing if the item is missing.
- 3) Decrease/increase in appetite/weight: the highest score recorded for the appetite/weight items: #6 (decreased appetite), #7 (increased appetite), #8 (decreased weight within the last two weeks), and #9 (increased weight within the last two weeks). This domain is missing if all items are missing or not applicable.
- 4) Concentration: Item #10 (concentration / decision making). This domain is missing if the item is missing.
- 5) Self-criticism: Item #11 (view of myself). This domain is missing if the item is missing.
- 6) Suicidal ideation: Item #12 (thoughts of death or suicide). This domain is missing if the item is missing.
- 7) Interest: Item #13 (general interest). This domain is missing if the item is missing.
- 8) Energy/fatigue: Item #14 (energy level). This domain is missing if the item is missing.
- 9) Psychomotor agitation/retardation: The highest score recorded for the two psychomotor items: #15 (feeling slowed down) and #16 (feeling restless). This domain is missing if all items are missing.

The QIDS-SR16 total score is the sum of the above domain scores. The total score will be missing if any domain score is missing.

The QIDS-SR16 total scores are categorized as follows:

- None (no depression): 0 – 5

- Mild: 6 – 10
- Moderate: 11 – 15
- Severe: 16 – 20
- Very severe: 21 – 27.

The following summaries will be produced for QIDS-SR16 total score category by treatment group for safety population during the Blinded Treatment Period (Period 2):

- The number and percentage of patients falling into each QIDS-SR16 total score category at each scheduled visit.
- Shift from maximum baseline to each post-baseline visit in QIDS-SR16 total score category.
- The number and percentage of patients falling into the following categories based upon the maximum post-baseline QIDS-SR16 total score:
 - Improved: maximum post-baseline category < maximum baseline category.
 - Worsened: maximum post-baseline category > maximum baseline category.
 - Same: maximum post-baseline category = maximum baseline category.

In addition, the number and percentage of patients falling into the following groups based upon the maximum post-baseline QIDS-SR16 item 12 (Thoughts of Death or Suicide) score will be summarized by treatment group for safety population during the Blinded Treatment Period (Period 2):

- Improved: maximum post-baseline QIDS-SR16 item 12 score < maximum baseline item 12 score.
- Worsened: maximum post-baseline QIDS-SR16 item 12 score > maximum baseline item 12 score.
- Same: maximum post-baseline QIDS-SR16 item 12 score = maximum baseline item 12 score.

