9.1. Determination of Sample Size

The total sample size for the study will be approximately 146 patients randomized at 1:1 ratio in the Blinded Treatment Period to ixekizumab Q2W and placebo (73 patients per treatment group).

No prior sPGA of Genitalia (primary outcome measure) data was available at the time of planning this study to guide sample size and power calculations because no biologic drug has been evaluated in a well-controlled clinical trial to date in patients with genital psoriasis. Therefore, based on the relevance and impact of sexual impairment in genital psoriasis, data from the assessment of DLQI Item 9 (How much has your skin caused any sexual difficulties?) outcomes in the ixekizumab Phase 2 and Phase 3 studies were used to calculate the sample size. Sample size was calculated assuming sexual impairment rates of 2% and 20% in the ixekizumab Q2W and placebo treatment groups, respectively. With these assumed rates, a sample size of 146 (73 per treatment group) is likely to achieve 94% power, based on a 2-sided Fisher's exact test at 0.05 level of significance.

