9.6. Safety Analyses

Safety will be assessed by summarizing and analyzing AEs including adjudicated cerebrocardiovascular events, QIDS-SR16, C-SSRS, laboratory analytes including neutrophil counts and immunogenicity, vital signs, and concomitant medications. The duration of exposure will also be summarized.

The primary safety analyses will focus on comparisons of ixekizumab Q2W versus placebo in Period 2. Treatment comparisons of categorical safety outcome variables will be performed using Fisher's exact test. Treatment comparisons of continuous safety outcome variables will be performed using ANCOVA with treatment and baseline value in the model.

Summaries of safety data collected during the Open-Label Treatment Period and Post-Treatment Follow-Up Period will be presented separately. The categorical safety measures will be summarized with incidence rates. The mean change of the continuous safety measures will be summarized by visits.

Unless otherwise specified, the baseline for safety analyses in the Open-Label Treatment Period is defined as the last nonmissing assessment on or prior to Week 12 (Visit 7). Unless otherwise specified, the Post-Treatment Follow-Up Period Baseline is defined as the last nonmissing assessment on or prior to Week 52 (Visit 12) or ETV.

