9.6.3. Vital Signs, Physical Findings, and Other Safety Evaluations

Vital signs will be presented as mean changes from baseline and as incidence of abnormal values and will be summarized for both predose and postdose at Week 0 (Visit 2) and Week 12 (Visit 7), as applicable.

The maximum postbaseline QIDS-SR16 total score will be summarized by treatment, and shift table will be produced for the change from baseline in QIDS-SR16 total score category.

Suicide-related thoughts and behaviors and self-injurious behavior with no suicidal intent, based on the C-SSRS, will be listed by patient.

Other covariate data, including body weight, will be descriptively summarized by treatment groups. Further analyses may be performed comparing the treatment groups.

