6.15. Safety Analyses

Safety will be assessed by summarizing and analyzing AEs including adjudicated cerebro-cardiovascular events, QIDS-SR16, C-SSRS, laboratory analytes, and vital signs. The duration of exposure will also be summarized.

For the Blinded Treatment Period (Period 2), safety data will be summarized using the safety population. Treatment group comparisons between ixekizumab Q2W and placebo will be performed on categorical safety data using a Fisher's exact test and continuous safety data will be analyzed by an ANCOVA model with treatment group and baseline as factors.

For the Open-label Treatment Period (Period 3), safety data will be summarized according to the treatment group to which they were assigned in Period 2 and Period 3 (i.e. IXE80Q2W/IXE80Q4W and PBO/IXE80Q4W) and overall.

For the Post-Treatment Follow-up Period (Period 4), safety data will be summarized according to the treatment group in Period 2 or Period 3 (i.e. prior to entering Period 4) as described in [Table RHBQ.6.1](#).

For safety analyses, the following baselines will be used:

- Treatment-emergent adverse events (TEAEs): baseline will be all results recorded during the baseline period (see Section 6.1.2 for definitions of the baseline period).
- Change from baseline to last observation and each scheduled post-baseline visit for laboratory and vital signs: baseline will be last non-missing assessment recorded during the baseline period (see Section 6.1.2 for definitions of the baseline period).
- Treatment-emergent abnormal laboratory and vital signs: baseline will be all results recorded during the baseline period (see Section 6.1.2 for definitions of the baseline period).
- Change from baseline to minimum or maximum: baseline will be all results recorded during the baseline period (see Section 6.1.2 for definitions of the baseline period).

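### SAP 6.15.6 plans only category summaries of the blinded-period QIDS-SR16 total, with no analysis of the score itself and no named test

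*SAP*

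**What the plan says.** SAP 6.15.6 describes the QIDS-SR16 as a means of assessing whether treatment affects depression, and defines a total of 0 to 27. It then bands the total as 0-5, 6-10, 11-15, 16-20 and 21-27. For Period 2 it states: "The following summaries will be produced for QIDS-SR16 total score category by treatment group". The outputs are counts per band at each visit, shifts from the maximum baseline band, and improved/worsened/same according to the band of the maximum postbaseline total. A further improved/worsened/same table covers item 12. No mean, change, confidence interval or test is specified.

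The general text is wider. Protocol 9.6 lists QIDS-SR16 among the safety measures and says: "Treatment comparisons of continuous safety outcome variables will be performed using ANCOVA with treatment and baseline value in the model". SAP 6.15 also lists QIDS-SR16. It assigns Fisher's exact test to categorical safety data in Period 2 and says that "continuous safety data will be analyzed by an ANCOVA model with treatment group and baseline as factors".

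The QIDS-specific protocol text, in 9.6.3, has two parts: "The maximum postbaseline QIDS-SR16 total score will be summarized by treatment", together with a shift table of score category. It does not mention ANCOVA.

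**The concern.** Depression is an adverse event of special interest (Protocol 8.2.2), and all patients receive ixekizumab from Week 12. The 12 blinded weeks are therefore the only randomized evidence on depressive symptoms. Banding discards movement within a band: a rise from 0 to 5 counts as unchanged, while a rise from 5 to 6 counts as worsened.

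The baseline rule blunts the comparison further. The Schedule of Activities has QIDS-SR16 at Visits 1, 2 and 7 only in this period. The maximum baseline is thus the higher of two readings, set against one scheduled postbaseline reading. A patient scoring 6 at screening, 5 at baseline and 10 at Week 12 is classed as the same, despite a 5-point rise from Week 0.

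The treatment of baseline is also uneven. SAP 6.7.1 summarizes the baseline total numerically and compares arms by ANOVA, but the postbaseline total, which carries the safety information, gets no numeric summary.

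**Working it through.** **Inputs from the documents.** Protocol 9.1 gives "approximately 146 patients randomized at 1:1 ratio", so 73 per arm. The score range and bands are in SAP 6.15.6.

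**The plan's own power figure.** Protocol 9.1 says the sample size "is likely to achieve 94% power, based on a 2-sided" Fisher's exact test at the 0.05 level. With 73 per arm and rates of 2% and 20%, exact enumeration gives 94.7% and the normal approximation 94.3%, so the figure reproduces. It concerns DLQI Item 9 and says nothing about QIDS-SR16.

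**Assumed inputs.** The documents give no QIDS mean, SD, correlation or effect size. Assumed here: mean/SD of 4/3.5, 5/4 and 7/4.5; baseline-to-Week 12 correlation 0.6; screening-to-baseline correlation 0.8 where the maximum-baseline rule is applied; two-sided alpha 0.05; a Week 12 score for all 73 patients per arm.

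**ANCOVA by formula.** Power = Φ( δ / (SD·√(1−ρ²)) · √(n/2) − 1.96 ). Here √(1−0.6²) = 0.8 and √(73/2) = 6.04. For δ = 1.5 points:

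| Mean/SD | δ in SD units | δ/(0.8·SD) | × 6.04 − 1.96 | Power |
|---|---|---|---|---|
| 4/3.5 | 0.43 | 0.536 | 1.28 | 90% |
| 5/4 | 0.375 | 0.469 | 0.87 | 81% |
| 7/4.5 | 0.33 | 0.417 | 0.56 | 71% |

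**Simulation.** Scores were rounded and clipped to 0-27, which lowers ANCOVA power slightly. The comparator is Fisher's exact test on the worsened category.

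| Uniform worsening | Baseline rule | ANCOVA | Fisher, worsened |
|---|---|---|---|
| 1.5 points | single baseline reading | 69-88% | 31-43% |
| 1.5 points | maximum of screening and baseline | 69-88% | 25-38% |
| 1 point | single baseline reading | 37-54% | 15-20% |
| 1 point | maximum of screening and baseline | 37-56% | 10-17% |

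A rank test on improved/same/worsened falls between the two: 31-57% for 1.5 points across both baseline rules.

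**Larger shifts.** These runs used skewed scores, mean/SD 4/3.5, 6/4.5 and 8/5, correlation 0.5 to 0.7, and the maximum-baseline rule:

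| Shift | ANCOVA | Fisher, worsened |
|---|---|---|
| 0.3 SD | 54-71% | 13-31% |
| 0.5 SD | 92-99% | 36-80% |
| 0.8 SD | at least 99.9% | 87-100% |

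At 0.5 SD the Fisher test is below 50% only for mean/SD 4/3.5 (36-40%). For the other two settings it is 56-80%.

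**A different alternative.** Suppose 10% of treated patients rise by 8 points and the rest do not change. ANCOVA then has 31%, 25% and 23% power for mean/SD 4/3.5, 5/4 and 7/4.5, against 17%, 16% and 13% for Fisher. The gain is 14, 9 and 10 points, and both methods would usually miss the signal.

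**The case against.** The strongest reply is that the plan is adequate and an ANCOVA is only a preference. It has four parts.

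- **A comparison may already be planned.** A reader might infer that the arms are not compared on QIDS-SR16 at all. The documents do not support that: the Fisher rule in SAP 6.15 is general and QIDS-SR16 is listed there. This stands. What remains is that 6.15.6 does not say so, while the laboratory and vital-sign sections restate their tests. Table RHBQ.6.6 also distinguishes Fisher-tested outputs from summaries and places the hepatic shift tables under summaries, so the word in 6.15.6 can be read either way.
- **The protocol does not prescribe ANCOVA for QIDS.** A reader might infer that the SAP departs from a QIDS-specific ANCOVA. It does not. The synopsis ties ANCOVA to vital signs and laboratory values, 9.6.3 asks for a summary and a shift table, and SAP 6.15 defines change-from-baseline baselines for laboratory and vital signs only. This also stands: the tension is between a general rule and specific text. The one QIDS-specific item lost is the numeric summary of the maximum total, which the SAP uses only to assign categories.
- **Other routes exist.** Depression and suicide/self-injury events are compared by Fisher's exact test in Period 2, item 12 is tabulated, and the C-SSRS is listed by patient. These are real safeguards. None measures graded change in depressive symptoms: the first needs a reported event, and the other two concern suicidality.
- **Bands are legitimate.** A patient-level shift table is a reasonable safety display, and any cut-point has a boundary. Agreed, which is why the tables should stay.

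**Conclusion.** The gap is real but modest. SAP 6.15.6 has no analysis of the score, no named test and no numeric summary of the maximum total, and it is silent on whether the general rule applies. Under the stated assumptions, a 1.5-point (0.33-0.43 SD) uniform worsening gives about 70-88% power with ANCOVA and about 25-43% with a Fisher test on the worsened category.

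A reader might go further and conclude that a moderate depression signal would probably be missed. The documents cannot show that, because they supply no QIDS distribution or effect size. The SAP's own convention for a moderate effect, in its psychometric section, is 0.5 SD. At that size the category test has 36-80% power, and in higher-scoring populations it would more often succeed than fail. The advantage of ANCOVA also shrinks when only a minority of patients deteriorate.

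The change is worth making because it is cheap and clearly more sensitive to a general shift in symptoms. It does not correct a breach of a QIDS-specific protocol requirement, apart from the missing summary of the maximum total.

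**What to change.** In SAP 6.15.6, for Period 2 and the safety population:

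1. Add change from baseline to Week 12 (or last observation) in QIDS-SR16 total score, compared by ANCOVA with treatment and baseline total score, with the treatment difference and its 95% CI.
2. Add descriptive statistics of the maximum postbaseline total score by treatment, as Protocol 9.6.3 specifies.
3. State that Fisher's exact test is applied to the proportion in the worsened category.
4. Keep the existing category, shift and item 12 tables.

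The data are already collected and the total is already scored, so the work is one added safety table plus a few descriptive rows. The statistical cost is one more unadjusted safety p-value, so the estimate and interval should carry the interpretation.
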